4.5 Special Consent Populations

A. Enrolling Minors-Subjects Who Are Not Yet Adults

- Parental Permission: N/A
- Non-Parental Permission: N/A
- Assent Process: N/A
- Documentation of Assent: N/A
- Reaching Age of Majority During Study: N/A

B. Enrolling Wards of the State

- Research Outside of NJ Involving Minor: N/A

C. Enrolling Non-English-Speaking Subjects

- Process for Non-English-Speaking Subjects: N/A
- Short Form Consent for Non-English Speakers: N/A

D. Enrolling Adults Lacking Decision-Making Capacity (Surrogate Consent)

- Assessing Adult Capacity to Consent: N/A
- Selecting a Surrogate & Consent Process: N/A
- Subject Assent: N/A
- Selecting a Witness to the Surrogate Consent Process: N/A
- Removing a Subject: N/A

E. Special Consent Consideration: N/A

4.6 Economic Burden and/or Compensation for Subjects

A. Expenses

The subjects will not incur any expenses specific to the research as the procedures are all part of standard medical care.

B. Compensation/Incentives

There will be no compensation or incentives for the subjects to participate in the study.

C Compensation Documentation

N/A

4.7 Risks of Harm/Potential for Benefits to Subjects

A. Description of Risks of Harm to Subjects

▪ **Reasonably Foreseeable Risks of Harm**

The use of blood flow restriction therapy carries a risk of developing late-onset muscle soreness, numbness, dizziness, and developing bruises under where the cuff for the tourniquet is placed. Muscle breakdown has also been reported in 0.008% of cases. (1)

▪ **Risk of Harm from an Intervention on a Subject with an Existing Condition**

N/A

▪ **Other Foreseeable Risks of Harm**

Data collected will be stored on REDCap. If these sources were to be breached, there is a risk of losing confidentiality for the subject.

▪ **Observation and Sensitive Information**

N/A

B. Procedures which Risk Harm to Embryo, Fetus, and/or Pregnant Subjects

N/A

C. Risks of Harm to Non-Subjects

N/A

D. Assessment of Social Behavior Considerations

N/A

E. Minimizing Risks of Harm

All paper documents containing data will be shredded by team members after recording the data points to REDCap. Access to REDCap will be limited to study member only and will be password protected. When it comes time for data analysis, the dataset will be exported from REDCap with the option to exclude any identifying material.

▪ Certificate of Confidentiality

N/A

▪ Provisions to Protect the Privacy Interests of Subjects

The subjects will only provide information to providers that they would by default provide information to at this institution, such as physicians and medical students regardless of whether they are participating in this study or not.

F. Potential Direct Benefits to Subjects

There are no direct benefits to subjects from their participation in this research.

5.0 Special Considerations

5.1 Health Insurance Portability and Accountability Act (HIPAA)

This study will utilize collect the identifying information previously listed. Authorization for PHI utilization is detailed in the written consent form.

5.2 Family Educational Rights and Privacy Act (FERPA): N/A

5.3 Code of Federal Regulations Title 45 Part 46 (Vulnerable Populations) : N/A

A. Special Populations

- Pregnant Persons or Fetuses: N/A
- Prisoners: N/A
- Neonates: N/A
- Neonates of Uncertain Viability: N/A
- Children: N/A
- Students/Employees: N/A
- Adults Lacking Decisional Capacity: N/A

5.4 General Data Protection Regulation (GDPR): N/A

5.5 NJ Access to Medical Research Act (Surrogate Consent): N/A

6.0 Data Management Plan

6.1 Data Analysis

RUBIES will conduct an a priori power analysis. The collected data will be analyzed with paired t-testing and Wilcoxon Ranked Sum Test to evaluate for significance.

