1.0 Research Design

1.1 Purpose/Specific Aims

To investigate the utility of using blood flow restriction (BFR) therapy in improving rotator cuff and proximal shoulder strength after surgical rotator cuff repair.

A. Objectives

This study aims to compare the improvements in range in motion and muscle strength between traditional therapy alone and BFR-augmented therapy during phase two of rehabilitation.

B. Hypotheses / Research Question(s)

Blood flow restriction in addition to outpatient physical therapy post-operative therapeutic exercise protocol will help to enhance muscle strength and endurance compared to post-operative therapeutic exercises alone.

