1.3 Research Design and Methods

A. Research Procedures

Potential subjects will be screened for possible inclusion in the study at the time of their evaluation by the surgeon during their clinic visit. Once they are seen for physical therapy, the physical therapist will review the study with the subject, answer any questions and consent patients who volunteer to participate in the study. Participants will be randomized to one of two groups. The control group receives standard post-operative physical therapy for rotator cuff repair and the experimental group receives the same standard therapy along with BFR therapy. BFR therapy entails the use of a tourniquet (blood pressure) cuff inflated to 50% of blood pressure occlusion, on the affected arm just distal to the affected shoulder, and then completing 4 sets of exercise with 30 seconds of rest in between. Use of BFR will occur along with physical therapy twice/week. Demographic data will be collected pre-operatively. Functional outcomes and PROMs will be collected 6 weeks into physical therapy, and repeated at 14 weeks into physical therapy.

B. Data Points

Range of motion, muscle strength, and muscle endurance is to be measured by approved physical therapists.

C. Study Duration

The study is expected to collect and analyze data for 2 years.

D. Endpoints

- Primary endpoints:
 - Isometric muscle strength
 - Muscle endurance
 - Shoulder Range of Motion
- Secondary endpoints:
 - Quick Disability of the Arms, Shoulder, and Hand (qDASH) score

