1.5 Sample Size Justification

Sample size estimation via a priori conducted by Rutgers RUBIS determined that at least 26 patients should be enrolled in this study..

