1.9 Data Collection

A. Primary Data Collection

- **Location:** Data will be collected during physical therapy visits at the UOA research sites.(Somerset, Wall, Morganville and Avenel). The data entry form that is completed after enrollment will be done in the clinic where the subject was consented. Data collection forms on REDCap will be completed during the physical therapy sessions by study members.
- **Process of Data Collection:**
Data will be collected by the specified team members. After enrollment to the study, the consenting team member will complete a data entry form that will record identifiers (name, email, phone number, race, gender and date of birth), gender, and date of surgery per the primary surgeon. After completing the specified physical therapy protocol per the study arm that the subject is assigned to, they will have range of motion (ROM) measured by a goniometer, muscle strength measured by a microFET 2 dynamometer, and muscle endurance measured by time to fatigue during exercise. qDASH questionnaires will be sent out to the subject and recorded to REDCap. All data collection will be done directly on REDCap.
- **Timing and Frequency:** Total duration of participation in this study will take 14 weeks. At the time of enrollment, demographic data will be collected. 6 weeks into post-operative physical therapy, functional outcomes (ROM, muscle strength, muscle endurance) and qDASH will be measured. At 14 weeks these same measures are repeated.
- **Procedures for Audio/Visual Recording:** N/A
- **Study Instruments:**
 - microFET 2 dynamometer
 - FDA Class II device
 - A handheld device that is used to measure muscle strength
 - The flat sensor is place of the muscle group to be tested, and then the subject flexes against the resistance of the device held against their limb
 - Device will record force in kilograms or pounds
 - Goniometer
 - FDA class I
 - A protractor designed to take measure joint angles
 - qDASH questionnaire
 - a validated questionnaire designed to assess how disability to the upper extremity affects quality of life.⁴
 - Intake Form
 - Form to be completed after enrollment to study
 - Will record subject identifiers (listed below), date of surgery, and gender
- **Ethnographic Studies, Interviews, Or Observation:** N/A
- **Subject Identifiers:**
 - name
 - Email
 - Phone number
 - Date of birth
 - Race
 - Gender

B. Secondary Data Collection

- **Type of Records:** N/A
- **Location:** N/A
- **Inclusion/Exclusion:** N/A

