4.3 Number of Subjects

A. Total Number of Subjects

We plan to enroll 26 subjects based on previous studies that also evaluated BFR. A priori power analysis with RUBIES will be conducted for a more concise target recruitment number.

B. Total Number of Subjects If Multicenter Study

26 subjects across all study sites.

C. Feasibility

This study protocol is feasible to execute given the prevalence of rotator cuff repairs that are surgically treated and the ease to which the data points can be collected.

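### The only parametric test named in section 6.1 is a paired t-test, which cannot compare BFR with control in two independent randomised arms

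*Protocol*

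**What the plan says.** The analysis plan is a single sentence in Protocol section 6.1: "The collected data will be analyzed with paired t-testing and Wilcoxon Ranked Sum Test to evaluate for significance". It does not attach either test to an endpoint or a contrast.

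The design and the question are set out elsewhere in the Protocol:

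- Section 1.3: "Participants will be randomized to one of two groups". One group has standard physical therapy, the other the same therapy plus BFR. No matching of patients and no crossover is described.
- Section 1.1, objective: to "compare the improvements in range in motion and muscle strength between traditional therapy alone and BFR-augmented therapy".
- Section 1.1, hypothesis: BFR added to therapy "will help to enhance muscle strength and endurance compared to post-operative therapeutic exercises alone".
- Section 1.9: function and qDASH are measured 6 weeks into physical therapy, and then "At 14 weeks these same measures are repeated".
- Section 1.5: a sample size estimation "determined that at least 26 patients should be enrolled in this study".

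**The concern.** The objective and the hypothesis are both contrasts between two sets of different patients. A paired t-test needs two linked observations per unit. Here the only link is between a patient's own week-6 and week-14 values, so the test asks whether patients changed over those 8 weeks. Patients in rehabilitation after a rotator cuff repair are expected to gain range and strength in either arm. A significant paired result in the BFR arm is therefore what one would expect even if BFR did nothing.

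The sentence also joins two tests that are not alternatives to each other. The non-parametric counterpart of the paired t-test is the signed-rank test, and the parametric counterpart of the rank-sum test is the independent-samples t-test. As worded, an analyst who judges the data normal and takes the t-test that is named would run no comparison of the arms. An analyst who takes the rank-sum test would run one. Which question is answered then depends on the look of the data. At stake is whether a recovery effect could be reported as a BFR effect.

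**Working it through.** **1. What each named test can do here**

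| Test in 6.1 | Data it needs | Use in this design | Tests BFR against control? |
|---|---|---|---|
| Paired t-test | Linked pairs | Week 6 to week 14 within patient | No |
| Wilcoxon rank-sum | Two independent samples | BFR arm against control arm | Yes |

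**2. Inputs for the illustration**

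From the Protocol: 26 patients in total and two arms. That total cannot be reproduced, because no alpha, power, effect size or SD is given; it is taken as it stands. Assumed: 1:1 allocation (13 per arm), two-sided 5%, normal data, no dropout, no BFR effect and the same recovery in both arms. The standardised change dz (mean change divided by the SD of change) has no source in the Protocol, so a range is shown.

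**3. Paired test in the BFR arm when BFR has no effect**

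The test has 12 degrees of freedom and noncentrality dz × √13. The probability of p < 0.05 comes from the noncentral t distribution.

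| dz | Noncentrality | Probability of significance |
|---|---|---|
| 0.6 | 0.6 × 3.606 = 2.16 | 51% |
| 1.0 | 1.0 × 3.606 = 3.61 | 91% |
| 1.5 | 1.5 × 3.606 = 5.41 | 99.9% |

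The control arm has the same probabilities. A simulation of 20,000 trials agrees at dz = 1.0: 91% in each arm, and 99.8% if all 26 patients are pooled into one paired test.

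**4. The rank-sum test between arms**

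In the same simulation, applied to change scores with equal change in both arms, the rank-sum test rejects in 4.3% to 4.5% of trials, so it holds its level. With a true arm difference of 1.2 SD of the change score its power is about 80% (independent-samples t-test: about 84%).

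**5. What a deciding between-arm test could detect**

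Detectable differences are for 80% power, two-sided 5% and 13 per arm, in units of the week-14 SD. Here r is the assumed correlation between week 6 and week 14, with equal SDs at both times.

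- Independent-samples t-test of week 14: 1.145 (noncentral t, 24 degrees of freedom).
- ANCOVA: 1.145 × √(1 − r²), ignoring the one degree of freedom spent on the covariate.
- t-test of change scores: 1.145 × √(2(1 − r)).

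| r | Week-14 t-test | Change-score t-test | ANCOVA |
|---|---|---|---|
| 0.5 | 1.15 | 1.15 | 1.145 × 0.866 = 0.99 |
| 0.7 | 1.15 | 1.145 × 0.775 = 0.89 | 1.145 × 0.714 = 0.82 |

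The ANCOVA and change-score columns apply only if the week-6 value is taken before BFR starts. Sections 1.3 and 1.9 do not say when BFR begins relative to that measurement.

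**The case against.** The best defence is that 6.1 does name a valid between-arm test. Read generously, the paired t-test describes change from week 6 to week 14 and the rank-sum test compares the arms, which fits the objective and the visit schedule. That reading is possible, and part of the defence stands. A reader might infer that the plan contains no test of BFR against control, or that the trial's question must go unanswered; the rank-sum test rules that out. A reader might also suspect that rank-sum was written in error for signed-rank, which would leave no between-arm test, but nothing in the text shows this.

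The Protocol also nowhere says that significance within an arm decides efficacy. The 51%, 91% and 99.9% figures price a misuse that the wording permits, not a rule that it sets. The same applies to any rate computed for BFR being significant while control is not.

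A separate statistical analysis plan may settle which test is decisive and whether to adjust for covariates, so silence on those matters is not the point. Nor is the lack of adjustment an error, since an unadjusted arm comparison is valid in a randomised trial. Against a change-score test at r = 0.7 the gain from ANCOVA is only 0.89 to 0.82 SD.

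What the defence does not remove is that the Protocol states a specific test, as its only parametric method, that does not fit its own design and objective.

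**Conclusion.** The point holds in this form: the paired t-test in 6.1 cannot test BFR against control, and it is coupled, on equal terms, with a rank-sum test that answers a different question. This rests on the wording of 6.1 set against 1.1 and 1.3, and needs no assumed figure.

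The size is conditional. If a paired result in the BFR arm were taken as evidence for BFR, the chance of a significant result with no BFR effect would be 51% to 99.9% over standardised changes of 0.6 to 1.5, against a nominal 5%. This assumes 13 per arm, two-sided 5% and equal recovery in both arms. If the rank-sum test between arms is the one used to judge BFR, the error rate is held at about 4.5% and the harm does not arise. The Protocol text does not secure that outcome, so it should be corrected before outcome data are examined.

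**What to change.** Replace the analysis sentence in section 6.1 with a paragraph to this effect:

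- **Deciding analysis.** Each continuous outcome at week 14 is compared between the randomised arms. If the week-6 measurement is taken before BFR starts, use ANCOVA with arm and the week-6 value as terms. If it is not, use an independent-samples t-test of the week-14 values, because adjusting for week 6 would then adjust for a value that treatment may have altered. Report the arm difference with its 95% confidence interval and two-sided p-value.
- **Supportive analysis.** A rank-sum test between arms: on the change from week 6 only if week 6 precedes BFR, otherwise on week-14 values.
- **Descriptive only.** Paired changes within each arm, not used to judge BFR.

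The Protocol must also state when BFR begins relative to the week-6 measurement, since that determines which version applies. The cost is one paragraph, with no new data, visits or patients. If week 6 precedes BFR, ANCOVA also brings the detectable difference below that of the week-14 t-test, to the extent shown in the working.

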1.10 Timetable/Schedule of Events

	Before Surgery	Surgery	Week 6 of PT	Week 14 of PT
Demographics	x			
Range of Motion (degrees)			x	x
Muscle Strength (kg)			x	x
Muscle Endurance			x	x
qDASH score			x	x

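### Section 6.1 fixes tests that cannot use covariates for a primary strength endpoint in unscaled kg; prespecified adjustment for sex and age, already recorded, could sharpen a valid but possibly imprecise comparison

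*Protocol*

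**What the plan says.** The analysis is described in one sentence of section 6.1: "The collected data will be analyzed with paired t-testing and Wilcoxon Ranked Sum Test to evaluate for significance". The protocol describes no adjusted model and no stratified randomisation; section 1.3 A says only that participants are randomised to one of two groups.

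Section 1.3 D lists "Isometric muscle strength" among three primary endpoints. In the schedule of events (1.10) the row label begins "Muscle Strength (kg", and section 1.9 says of the dynamometer: "Device will record force in kilograms or pounds". No scaling to body size or to the other arm is stated. Section 4.1 C admits adults from 18 years, with no upper age limit and no restriction by sex.

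On sample size, section 1.5 says that an a priori estimation "determined that at least 26 patients should be enrolled in this study", while section 4.3 says "We plan to enroll 26 subjects based on previous studies that also evaluated BFR" and places the power analysis in the future. Either way the planned total is 26.

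The entry form completed after enrolment will "record identifiers (name, email, phone number, race, gender and date of birth), gender, and date of surgery". Date of birth, race and gender also appear in the list of subject identifiers in 1.9. For analysis, section 4.7 E says "the dataset will be exported from REDCap with the option to exclude any identifying material".

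**The concern.** Force in kg can be expected to differ between men and women and across adult ages. A test without covariates leaves that variation in the error term. With about 13 patients per arm, a chance difference in the sex mix also moves the estimated BFR effect on week-14 levels. The interval allows for this, but only by being wider than an adjusted one would be if sex and age are prognostic.

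The named tests are the obstacle. Replacing the paired t-test, which does not compare two independent arms, with a two-sample t-test would still leave no place for a covariate. At stake is precision in a small trial, and whether adjustment is settled before the results are seen.

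**Working it through.** **Inputs from the protocol:** total 26 (1.5, 4.3); strength in kg (1.10); tests without covariates (6.1); outcomes at weeks 6 and 14 of physical therapy (1.3 A, 1.10).

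**Assumptions, not in the documents:** 1:1 allocation, so 13 per arm; two-sided 5%; R-squared, the share of within-arm variance in week-14 strength explained by sex and age; 13 men and 13 women for the imbalance figures.

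**The plan's own figure.** No alpha, power, effect size, SD or allocation ratio is given, so 26 cannot be reproduced. With 13 per arm, an unadjusted two-sample t-test has 80% power for a difference of about 1.15 SD (noncentral t, 24 df).

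**Interval width for week-14 levels, adjusted over unadjusted.** Two covariates cost 2 df and inflate the variance of the arm effect, on average, by (26 − 3)/(26 − 3 − 2) = 23/21 = 1.095. The critical values are 2.074 (22 df) and 2.064 (24 df), a ratio of 1.005.

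Ratio = sqrt((1 − R²) × 1.095) × 1.005

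| R² | Ratio | Interval |
|---|---|---|
| 0 | 1.05 | 5% wider |
| 0.20 | 0.94 | 6% narrower |
| 0.35 | 0.85 | 15% narrower |
| 0.50 | 0.74 | 26% narrower |

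Break-even: (1 − R²) × 1.095 × 1.005² = 1, so R² is about 0.10. A simulation (8,000 runs per scenario, true difference 1.14 SD) gave the same four ratios. Power went from 0.79 to 0.84, 0.79 to 0.90 and 0.80 to 0.96 for R² of 0.20, 0.35 and 0.50, and from 0.81 down to 0.77 for R² of 0.

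**What R² might be.** With half the patients men and a sex gap of g within-sex SDs, sex alone gives R² = 0.25g²/(1 + 0.25g²). For g = 0.5, 1, 1.5 and 2 this is 0.06, 0.20, 0.36 and 0.50. A gap of half an SD would not by itself reach break-even.

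**Chance imbalance in sex** (26 patients, 13 men, 13 per arm):
- P(arms differ by 3 or more men) = 1 − 2 × C(13,6)²/C(26,13) = 1 − 2 × 1716²/10,400,600 = 0.434.
- P(differ by 5 or more) = 0.434 − 2 × 1287²/10,400,600 = 0.115.
- An 8 versus 5 split moves the unadjusted difference in levels by 8/13 − 5/13 = 3/13, or 23% of the male-female gap.

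**If change is analysed instead.** Suppose sex adds the same g kg at both visits. Then week 14 minus week 6 contains g − g = 0, and neither the loss of precision nor the 23% shift arises from that source. Only sex or age differences in the gain itself would remain.

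**Sex and age against the week-6 value.** The table shows power at a true difference of 0.8 week-14 SDs, where unadjusted levels give 50%. It assumes equal SDs at both visits and correlation r between them. The variance factor is 2(1 − r) for change, and (1 − r²) × 23/22 with 23 df for a model with week 6 as the covariate.

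| Analysis | Assumption | Power |
|---|---|---|
| Levels adjusted for sex and age | R² = 0.20 / 0.35 / 0.50 | 55% / 64% / 75% |
| Change | r = 0.5 / 0.7 / 0.8 | 50% / 71% / 87% |
| Levels adjusted for week 6 | r = 0.5 / 0.7 / 0.8 | 60% / 76% / 89% |

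The last two rows are clean only if week 6 comes before BFR. Section 1.1 A refers to phase two of rehabilitation. Section 1.3 A gives BFR twice a week without a start. Section 1.9 places the measurements after completion of the arm's therapy protocol, yet at weeks 6 and 14. The order cannot be read from the text.

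**The case against.** Four objections carry weight.

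**Covariates are usually chosen in the SAP.** True, and a missing covariate list would be no finding. But section 6.1 names the tests, and a later regression would depart from them. The point is limited to that commitment.

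**Unadjusted randomised comparisons are valid.** This stands in full. Chance imbalance is already within the 5% error rate and the interval. A reader might infer from the 43% figure that the result would be biased or misleading; the figure describes ordinary sampling variation and supports only a claim about precision.

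**The objective in 1.1 A concerns improvements.** This also stands. A constant sex difference cancels in change, so the gains above belong to week-14 levels. A model of levels on arm, sex and age alone would drop that objective, and could be less precise than change analysis when the two visits are well correlated.

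**The export clause does not remove the data.** A reader might infer from 1.9 and 4.7 E together that the analysis file will lack age and sex, so that no later plan could adjust. The text does not support that. Exclusion is an option; 1.9 lists gender a second time outside the identifier bracket; and under 6.2 the data stay on REDCap for 6 years, so a second export is possible. Nor are age and gender the only patient data recorded at entry: race and date of surgery are recorded too, and date of surgery is not on the identifier list. What remains is an ambiguity worth one sentence.

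**Conclusion.** The point holds as a cheap improvement, not as an error that invalidates the comparison. Section 6.1 commits a trial of about 26 patients to tests that cannot use sex and age, although both are recorded and a primary endpoint is in unscaled kg.

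The size depends on an R-squared that the documents do not give, and on levels being compared. The range runs from a 26% narrower interval at R² of 0.50, through no gain near 0.10, to one 5% wider at zero. For change scores the gain is smaller and may be nil. No case is made here for the same covariates in endurance, range of motion or qDASH.

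**What to change.** 1. **Section 6.1.** Make the between-arm comparison of strength a linear regression on arm with sex and age at enrolment as prespecified covariates. Report the adjusted difference with its 95% confidence interval, and keep the rank-sum test as a sensitivity analysis.
2. **Week-6 value.** State in the protocol how the week-6 assessment stands in time to the start of BFR. If week 6 is confirmed to precede BFR, include the week-6 value as a further covariate (or analyse change), which keeps the improvements objective. If it is not confirmed, adjust for sex and age only, since treatment cannot alter them.
3. **Section 4.7 E (minor).** State that age in years, derived before export, and gender stay in the coded analysis file.

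The cost is wording in two sections and one clarification of timing, with no new data, visits or patients. The statistical price of sex and age is 2 degrees of freedom and an interval about 5% wider if they prove unrelated to strength; the week-6 value, if used, costs one more.
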